#### **7.2.1.2. Subgroup Analysis**

No subgroup analysis is planned for primary endpoint.

#### **7.2.1.3. Multicenter Studies**

No center-specific summary will be produced. Data from all centers will be pooled together.

#### **7.2.1.4. Hypothesis Testing and Significance Level**

No formal hypothesis testing will be performed.

#### **7.2.1.5. Sensitivity Analyses**

Observed response rates (without any imputation) at Day 28 will be tabulated along with 95% Clopper-Pearson exact confidence intervals. In addition, both imputed and observed results will be presented at all study visits.

### **7.2.2. Other Efficacy Analyses**

#### **7.2.2.1. Acute GI-GVHD response, acute GVHD response (all organ), Very Good Partial Response, Treatment Failure**

Number (%) of responders according to the following response criteria will be calculated at for all visits along with 95% Clopper-Pearson exact confidence intervals (CIs) for both observed and imputed summaries:

- Acute GI GVHD Response Criteria (complete response, partial response, mixed response, no response and progression)
- Acute GVHD Response Criteria involving all organs (complete response, partial response, mixed response, no response and progression)

### **Imputation technique for missing acute GI-GVHD and all organ-GVHD response**

- There could be two types of missing data
  - Missing data at intermediate visits (for example, patient may miss Day 28 visit but still has data on Day 21 and 35).
  - Missing data due to discontinuation or deaths.
- Imputations will be performed up to Day 180 visit (maximum visit for stage data)
- For missing visits due to death, all subsequent visits will be imputed as “progression” (irrespective of secondary therapy); note, the protocol defined visit windows can be either  $\pm 2$  or  $\pm 15$  days depending on whether they fall in the treatment-period vs. follow-up period. However, the analysis windows are wider than protocol defined visit windows; if death occurs within a pre-specified analysis window for a particular visit (even if the target day for that visit is less than the day of death), missing values will be considered as ‘progression’.
  - Example: non-missing responses on Day 7, secondary therapy starting on Day 9, death on day 10, Day 14 onward – impute as progression.
- If all post-baseline responses are missing due to an early death, then missing responses will be imputed as “progression”.
- For other missing visits, following imputation rules will be implemented:
  - If the previous observed response is “Progression”, then subsequent missing visits will be imputed as “Progression” irrespective of secondary therapy
  - If response is not “progression” at the previous visit and a patient has been administered with secondary therapy since then, all subsequent missing visits will be imputed as NR
    - Example: Day 14 is CR, Day 28 and Day 35 visits are missing
      - If no secondary therapy flag before Day 28, then Day 28 response will be imputed as CR
      - If secondary therapy administered before Day 28, both Day 28 and 35 missing responses will be imputed as NR
  - Otherwise, carry forward the last non-missing response. Only post-baseline responses are carried forward. If first post-baseline response is missing and the patient did not die, no response can be carried forward.

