6.5.4. Stopping Guidelines for Excessive Mortality

Mortality of 40% at Day 56 would be considered unexpected and an unacceptable number of excess deaths compared to the anticipated and historical rate of approximately 20% (data on file). Therefore, a stopping rule for Day 56 mortality will be applied after every 6 subjects are accrued. The study will be stopped at interim evaluation (t) if the number of deaths is ≥Xt, eg, if 4 or more deaths in the first 6 subjects or 6 or more deaths in the first 12 subjects, etc, as detailed in Table 7 below. A 20% mortality rate, which is anticipated based on historical data, will have a 2.6% chance of triggering the stopping rule for mortality. If a mortality rate of 40% is observed, a 20% increase in mortality over the historical rate, there will be a 71.0% chance of triggering the stopping rule with 30 subjects.

Table 7: Cumulative Stopping Probabilities for Mortality Rates at Day 56

Evaluation (t)	Total N	Xt	Cumulative Probabilities of Stopping at Evaluation (t) with Observed Mortality Rates					
			0.20	0.40				
1	6	4	1.7%	17.9%				
2	12	6	1.9%	33.5%				
3	18	8	1.6%	43.7%				
4	24	10	1.3%	51.0%				

Evaluation (t)	Total N	Xt	Cumulative Probabilities of Stopping at Evaluation (t) with Observed Mortality Rates					
			0.20	0.40				
5	30	11	2.6%	71.0%				

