13.7.2. Acute GI GVHD Response Criteria

Acute GI GVHD response criteria will be based on the proportion of subjects with CR, PR, MR, NR and Progression and will be summarized by visit along with 95% CIs.

Subjects who discontinue from the study early will be imputed as having no response.

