#### 5.1.1. Primary Endpoint(s)

The primary efficacy endpoint is the overall acute GVHD response at Day 28. The overall acute GVHD response is defined as improvement from Baseline in any organ (skin, lower GI tract and liver) by at least 1 stage, without progression in any other organ and with no additional therapy being administered. Baseline will be defined as the stage value determined at the diagnosis i.e. the first value recorded prior to 1st ALXN1007 infusion. At every visit, patients will be graded according to the Modified Keystone Grading Schema displayed in **Table 2**.

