## 5.1.2. Other Efficacy Endpoints

### 5.1.2.1. Acute GI GVHD response

Acute GI-GVHD responses will be derived based on the following order (Progression, NR, MR, PR and CR) and these responses are mutually exclusive. The effect of secondary therapy only needs to be applied to 'NR' and no need to apply separately to MR, PR and CR because of inherent ordering.

- **Progression:** deterioration in lower GI tract staging (positive change from baseline).
- **No Response (NR):** no change in lower GI tract staging OR receiving secondary therapy.
- **Mixed Response (MR):** improvement in lower GI tract AND deterioration in another organ.
- **Partial Response (PR):** improvement in lower GI tract (provided lower GI tract staging is not 0) AND no deterioration in another organ.
- **Complete Response (CR):** lower GI tract Stage = 0

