#### **7.2.1.1. Handling of Dropouts or Missing Data**

- Imputations will be performed up to Day 180 visit (maximum visit for stage data)
- If a patient has been administered with secondary therapy or died before the next missing visit, all subsequent missing values will be imputed as NR (non-responder), otherwise, last non-missing response will be carried forward.

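### The imputed GI and all-organ response tables code death from any cause as Progression, so that row mixes mortality with stage worsening

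*SAP*

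**What the plan says.** **Definition of Progression.** SAP 5.1.2.1 defines GI Progression as "deterioration in lower GI tract staging (positive change from baseline". SAP 5.1.2.2 defines all-organ Progression in the same way: at least one organ worse and none better. Death is part of neither definition. Protocol 10.2.3 and SAP 5.1.2.4 list Progression and mortality as separate items within treatment failure.

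**Imputation in the two categorical tables (SAP 7.2.2.1).** "For missing visits due to death, all subsequent visits will be imputed as" progression, irrespective of secondary therapy and of cause, up to Day 180. Subjects with no post-baseline data are handled alike: "If all post-baseline responses are missing due to an early death, then missing responses will be imputed as" progression. There is also a window clause. The SAP codes a missing visit as progression "if death occurs within a pre-specified analysis window for a particular visit", even when the target day comes before the death.

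**Imputation in the primary analysis (SAP 7.2.1.1).** If the subject received secondary therapy or "died before the next missing visit, all subsequent missing values will be imputed as NR (non-responder"; otherwise the last response is carried forward. There is no window clause. The primary endpoint is binary (SAP 5.1.1): "improvement from Baseline in any organ (skin, lower GI tract and liver) by at least 1 stage, without progression in any other organ". Any added treatment also rules out a response.

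**Protocol rule (13.7.2).** "Subjects who discontinue from the study early will be imputed as having no response". SAP 4.1 discloses that this rule was changed but gives no reason.

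**Endpoints affected (Protocol 5.2.2).** The proportion with Progression is listed for GI at Day 28 and for all organs at Days 14, 28 and 56. SAP 7.2.2.1 tabulates both at all visits, as observed and as imputed summaries.

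**The concern.** A death is a known outcome. It is not a missing stage, and it is not in itself evidence that the gut, skin or liver got worse. A subject in complete GI response who dies of infection or relapse appears in the imputed table as GI GVHD progression from that point on. In a small study of a drug given for lower GI GVHD, a reader will want to separate uncontrolled GVHD from death by another route. The imputed Progression row cannot do that.

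The matter is sharper by cohort. SAP section 7 presents summaries by dose group, and Protocol 6.2 plans 3 to about 6 subjects in each of Cohorts 2 and 3. One death in a subject who had not progressed adds 1/6 = 17 to 1/3 = 33 percentage points of Progression to such a group.

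**Working it through.** Neither document gives an expected Progression proportion, so there is no planned figure to reproduce.

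**Inputs**
- *m*, mortality by the visit. For Day 56, Protocol 6.5.4 calls 40% unacceptable "compared to the anticipated and historical rate of approximately 20% (data on file"), so *m* = 0.20. No Day 28 figure is given. A constant hazard through the Day 56 value is assumed: *m* = 1 − 0.80^(28/56) = 10.6%.
- *p*, Progression among survivors. It is not stated; 5% to 40% is assumed.

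**Share of the imputed row that is deaths.** With every death coded as Progression, the row is *m* + (1 − *m*)*p*, and the share due to deaths is *m* / [*m* + (1 − *m*)*p*]. At Day 56:

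| *p* | Progression row | Share due to deaths |
|---|---|---|
| 5% | 0.20 + 0.80 × 0.05 = 24% | 83% |
| 10% | 0.20 + 0.80 × 0.10 = 28% | 71% |
| 20% | 0.20 + 0.80 × 0.20 = 36% | 56% |
| 30% | 0.20 + 0.80 × 0.30 = 44% | 45% |
| 40% | 0.20 + 0.80 × 0.40 = 52% | 38% |

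Deaths exceed half the row when *p* < *m*/(1 − *m*) = 0.20/0.80 = 25%. At Day 28, under the constant-hazard assumption, the share runs from 70% (*p* = 5%) to 23% (*p* = 40%), and the break-even *p* is 11.8%.

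**Points added by the rule.** The comparison is with carrying forward the last staged category. A subject already in Progression at death would stay there anyway. If *q* is the share of the deceased already in Progression, the rule adds *m*(1 − *q*) at Day 56: 20 points for *q* = 0 and 0.20 × 0.5 = 10 points for *q* = 0.5.

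**Illustration.** N = 30, 6 deaths by Day 56 (20%), an assumed 3 survivors in Progression, none of the deceased already in Progression; Clopper-Pearson 95% intervals:
- SAP imputed table: 9/30 = 30.0% (14.7 to 49.4).
- Observed table, if the dead leave the denominator: 3/24 = 12.5% (2.7 to 32.4).
- Stage-based Progression over all 30: 3/30 = 10.0% (2.1 to 26.5). Neither planned table shows this figure.

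**The two death rules side by side.** Take a weekly-dosed subject with partial response at Day 21, Day 28 missing, no secondary therapy, and death on Day 30.
- All-organ table: Day 30 is within 2 days of Day 28, the protocol window for weekly dosing, and SAP 7.2.2.1 says its analysis windows are wider. Day 28 is Progression.
- Primary: the death does not precede the missing Day 28 visit, so the partial response is carried forward and the subject is a responder.

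The SAP text does not give the analysis-window limits, so how often this could happen cannot be worked out.

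**The case against.** The strongest defence is that putting death in the worst category is pre-specified, conservative and cannot inflate response. The protocol itself groups progression and mortality under treatment failure. The study is descriptive, with no hypothesis test, and no decision rule uses the Progression row. Observed tables are planned beside the imputed ones. Overall survival, non-relapse mortality with relapse-related death as a competing risk, adverse events leading to death and by-patient staging listings are also planned. All of this is correct, and it means the planned outputs taken together do hold information on deaths.

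It does not settle the point. The observed tables impute nothing after death, so they presumably condition on being alive; the SAP does not state their denominator. Survival and non-relapse mortality are estimated at Days 180 and 360, not at Days 14, 28 or 56. Stages are listed only, and treatment failure, where combining death with progression is explicit, is not analysed for the abbreviated report.

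Three stronger readings are tempting and not supported:
- A reader might infer that reported Progression is largely a mortality count. That depends on a survivor progression rate the documents do not give, and it concerns only the imputed tables.
- A reader might infer that non-response in the primary and Progression in the other tables give conflicting response rates. Both labels are non-response, so apart from the window clause the difference is one of name.
- A reader might infer an undisclosed departure from the protocol. SAP 4.1 discloses the change.

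**Conclusion.** The concern holds for the imputed tables. Death from any cause is coded as Progression, against the SAP's own staging definitions and its separate listing of mortality. The listed endpoints affected are GI Progression at Day 28 and all-organ Progression at Days 14, 28 and 56. The Day 56 inflation of up to 20 points rests on the protocol's 20% mortality and on none of the deceased having progressed before death. The 38% to 83% share of deaths also rests on the assumed 5% to 40% among survivors, and the Day 28 range further assumes a constant hazard. Complete, partial and overall response are untouched by the label.

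The window clause is a separate, real mismatch: it can make one subject Progression in the all-organ table and a responder in the primary at the same visit. Both matters are worth correcting, but in a descriptive study neither undermines the primary result.

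**What to change.** 1. In SAP 7.2.2.1, for visits missing because of death (including subjects with no post-baseline response), replace the progression code by a separate Died category in both imputed tables. Keep these subjects in the mFAS denominator as non-responders. The Progression row then holds only observed or carried-forward stage deterioration in subjects not recorded as dead for that visit. A footnote can give how many of those in the Died row were last staged as Progression.
2. In SAP 7.2.1.1, adopt the same death and analysis-window rule, and state the window limits. A missing visit with a death inside its window is then Died in the all-organ table and non-response in the primary.

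The cost is one more row in two tables and a few sentences in the SAP. Item 1 leaves complete, partial and overall response unchanged. Item 2 may make the primary rate slightly less favourable where the window rule applies.

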#### **7.2.2.1.1. Individual Staging Score, Skin Rash BSA and Stool volume**

A by-patient listing for these parameters will be produced. No tabular summaries will be generated.

#### **7.2.2.2. Overall Survival**

Kaplan-Meier estimate of survival rate at Day 180 and 360 along with 95% CI (using loglog transformation) will be summarized. Patients who are still alive as of the last known follow-up will be right censored as of the time point of analyses. Estimated time (days) of death based on KM method will be provided for 25th, 50th (i.e. median) and 75th percentile along with 95% CI.

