6.1.3. Follow-up Period (Day 86 - Day 180)

Subjects will return to the site for follow-up visits on Days 86 and 180 following Baseline. Each follow-up visit should occur within ± 15 days of the planned date.

The evaluations that will occur during the Follow-up Period (Days 86 and 180) include the following: acute GVHD staging, physical exam (Day 180 only), ECG (Day 180 only), vital signs, weight, laboratory tests, pregnancy test (for women of childbearing potential), PK/PD (see Table 5), antibodies to ALXN1007, exploratory biomarkers, and recording of AEs (see Section 11.2) and concomitant medications and therapies (see Section 8.2).

6.1.4. Survival Status on Day 360

Subjects and/or their caregivers will be contacted by the site on Day 360 (± 15 days) following Baseline. Questions regarding the subject's survival status will be asked of the subject and/or the caregiver by telephone call.

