6.5.2. End of Study for All Patients

The study will end when all treated subjects have either completed the Day 360 data collection, the ET visit, or are documented as lost to follow-up.

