13.7.5. Overall Survival

Overall survival will be summarized using date of first study treatment with ALXN1007 up to Days 180 and 360 via the use of the Kaplan-Meier method, and 95% CIs will be calculated.

Subjects who are still alive as of the last known follow-up will be right censored as of the date of last subject contact.

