### **4.1. Changes from Analyses Specified in the Protocol**

Following changes in analyses specified in the protocol are noted:

- Safety analyses will be only performed on safety set as opposed to both safety set and modified safety set as mentioned in the protocol.
- Demographics, baseline characteristics and medical history will be only summarized for safety set as opposed to safety set, modified full analysis set and per-protocol set as mentioned in the protocol.
- The imputation rule has been modified from that described in the protocol for overall acute GVHD response, acute GI-GVHD response and acute GVHD response involving all organs.

In addition due to early termination of the study, an abbreviated CSR will be written and a number of pre-specified analyses will not be performed however by-patient listings will be generated for all data collected for this study.

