#### **5.1.2.8. Overall Survival**

Assessment of overall survival at Days 180 and 360 will be measured based on the time (days) since 1st ALXN1007 dose to death due to any reason. Patients with incomplete follow-up for other reasons will be censored.

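### The SAP censors survivors at the time of analysis, not at last contact, so anyone lost to follow-up is counted as alive and overall survival is biased upward

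*SAP*

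**What the plan says.** Protocol 13.7.5 sets the rule for survivors: "Subjects who are still alive as of the last known follow-up will be right censored as of the date of last subject contact". SAP 7.2.2.2 keeps the sentence but changes the date: "Patients who are still alive as of the last known follow-up will be right censored as of the time point of analyses". The SAP does not define that time point.

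The estimator is given in the same SAP section: "Kaplan-Meier estimate of survival rate at Day 180 and 360 along with 95% CI (using loglog transformation) will be summarized". Quartiles of survival time are also to be reported.

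SAP 5.1.2.8, which defines the endpoint, adds: "Patients with incomplete follow-up for other reasons will be censored". It gives no censoring date.

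SAP 4.1 lists three changes from the protocol: the safety analysis set, the set for demographics and history, and the response imputation rule. Overall survival censoring is not among them. SAP 4.2 only points back to 4.1.

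**The concern.** Censoring at last contact removes a subject from the risk set when information about that subject stops. Censoring at a later analysis date treats the unobserved interval as observed survival. If every subject without a recorded death is carried to the landmark, the Kaplan-Meier estimate becomes 1 − (observed deaths ÷ N), as if all lost subjects were known to be alive.

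The documents provide for incomplete follow-up. Protocol 6.5.2 lets the study end for subjects who complete an early termination visit "or are documented as lost to follow-up". Protocol 7.3.2 covers withdrawal of consent. Day 360 status rests on a telephone contact (Protocol 6.1.4): "Questions regarding the subject's survival status will be asked of the subject and/or the caregiver by telephone call". The trial also stopped early; SAP 4.1 says that "due to early termination of the study, an abbreviated CSR will be written".

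Overall survival is one of the few efficacy endpoints still estimated in that report. Very good partial response, treatment failure and flares are dropped, and steroid dose and immunosuppressant discontinuation are reduced to listings. With no comparator and no hypothesis test, the survival estimate and its interval are themselves the result.

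**Working it through.** The plan states no overall survival rate and no dropout rate, so there is no figure of its own to reproduce. The check compares the two censoring dates.

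**Direction.** The estimator is S(t) = Π (1 − dᵢ/nᵢ) over death times up to t. Moving a censoring date later leaves each dᵢ unchanged and can only increase nᵢ, so no factor falls. S(t) is strictly higher when at least one subject is lost before a later death. If all survivors are carried to the landmark τ, the mean excess over true survival equals P(lost before death, and death by τ).

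**Worked case.** Inputs: N = 30 (SAP 4, approximately 30 subjects) and 20% dead by Day 56 (Protocol 6.5.4, historical rate). Assumed: deaths on Days 10, 20, 30, 40, 50, 56, 100, 140, 170, 200, 250 and 300; six subjects lost at Day 60; all others followed to Day 360. The SAP rule is read as censoring at Day 360.

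- Both rules at Day 56: 24/30 = 0.800.
- Last contact: 24 − 6 = 18 at risk at Day 100. Day 180: 0.800 × 15/18 = 66.7%. Day 360: 0.800 × 12/18 = 53.3%.
- SAP rule: 24 at risk at Day 100. Day 180: 0.800 × 21/24 = 70.0%. Day 360: 0.800 × 18/24 = 60.0%, which is 1 − 12/30.
- With three lost at Day 60, last contact gives 0.800 × 18/21 = 68.6% and 0.800 × 15/21 = 57.1%; the SAP rule again gives 70.0% and 60.0%.
- With none lost, both rules give 70.0% and 60.0%.

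**Interval at Day 360, six lost.** With single deaths the Greenwood sum is Σ 1/[n(n−1)], and the log-log limits are S raised to exp(±1.96 × √sum ÷ |ln S|).

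- Last contact: (1/24 − 1/30) + (1/12 − 1/18) = 0.0361. The 95% CI is 32.1% to 70.6%, width 38.5 points.
- SAP rule: 1/18 − 1/30 = 0.0222. The 95% CI is 40.5% to 75.0%, width 34.5 points.

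**Simulation.** 2,000 trials per scenario, N = 30, 20% dead by Day 56, loss independent of death at a constant rate. The Day 180 and Day 360 survival rates and the loss rates are assumed. Mean Day 360 estimate, last contact against SAP rule:

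| True Day 360 survival | 10% lost by Day 360 | 20% lost | 30% lost |
|---|---|---|---|
| 60% | 59.8 vs 61.0 | 59.9 vs 62.4 | 60.2 vs 64.1 |
| 50% | 50.0 vs 51.5 | 50.2 vs 53.3 | 50.4 vs 55.3 |
| 40% | 40.2 vs 42.1 | 39.9 vs 43.9 | 40.0 vs 46.1 |

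The Day 180 shift is about 0.5 to 4 points. In no simulated trial was the SAP estimate below the last-contact estimate. Earlier losses make the shift larger: with losses spread uniformly over Days 7 to 180 and true Day 360 survival of 50%, the SAP rule gives about 52.5% at 10% loss and about 58% at 30% loss.

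**The case against.** The strongest objection is that the disputed phrase is undefined. SAP 5.1.2.8 says incomplete follow-up is censored, so one could assign lost subjects to that section and leave 7.2.2.2 for those followed to the landmark. The text does not allow this split: 7.2.2.2 covers everyone alive at last known follow-up, which includes subjects lost while alive, and 5.1.2.8 supplies no date. Reading the phrase as the data cut is correct for a subject known to be alive at the cut, but it still credits unobserved survival to one lost earlier. It remains possible that the sponsor meant last contact; the SAP does not say so.

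The size is also open to challenge, and part of this stands. The loss rates are assumptions. Subjects who stop treatment are asked to attend through Day 180, and non-returners are traced by three calls and a registered letter (Protocol 7.3.2). Subjects without biopsy confirmation are outside the modified full analysis set and cannot affect the estimate. At 50% survival and N = 30, the approximate 95% half-width is 1.96 × √(0.25/30) = 17.9 points, so a shift of a few points is small beside sampling error. Unlike sampling error, though, it always runs in the favourable direction.

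Finally, no test or stopping decision uses this estimate, and by-patient listings would let a reader check the censoring. That limits the consequences but does not make the rule correct.

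For non-relapse mortality the disputed wording does not appear. Including it in the fix is a matter of consistency only.

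**Conclusion.** The concern holds. SAP 7.2.2.2 replaces the protocol's censoring date with a later one, SAP 4.1 does not declare the change, and nothing else in the SAP restores the protocol rule. The direction is certain: survival estimates can only stay the same or rise. The size depends on how many subjects were lost before later deaths, which the documents do not give. Under an assumed 10% to 30% loss by Day 360, independent of death, the mean shift at Day 360 is about 1 to 6 points. It is larger if losses come early, 6.7 points in the worked case with six of 30 lost at Day 60, and zero with complete follow-up. The interval also narrows, because unobserved time is counted as exposure.

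**What to change.** In SAP 7.2.2.2, censor subjects not known to have died at the date last known alive, or at Day 180 or Day 360 if follow-up extends beyond that landmark. State the same date in SAP 5.1.2.8.

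Apply it to non-relapse mortality as well. SAP 5.1.2.9 censors without a date, and SAP 7.2.2.8 refers to a flare method that the SAP does not contain. The flare method in Protocol 13.7.6 already uses last contact, so this only makes the rule explicit.

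If the sponsor wants a different censoring date, it should be defined, listed in SAP 4.1 and justified.

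The cost is one sentence plus matching cross-references. The protocol rule already requires the last-contact date, so no new data are needed. The reported survival may be slightly lower and its interval slightly wider.
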